7.2.2. Graded Laboratory Values

The CTCAE Version 4.03 will be used for assigning toxicity grades (0 to 4) to laboratory results for analysis. Grade 0 includes all values that do not meet the criteria for an abnormality of at least Grade 1. For laboratory tests with criteria for both increased and decreased levels, analyses for each direction (ie, increased, decreased) will be presented separately.

7.2.2.1. Treatment-Emergent Laboratory Abnormalities

Induction Studies (Cohort A Induction Study and Cohort B Induction Study)

Treatment-emergent laboratory abnormalities are defined as values that increase at least 1 toxicity grade from baseline at any postbaseline time point, and

- No later than 30 days after the last dosing date of Induction Study, for subjects who did not take any study treatment from Maintenance Study, or
- On or before the first dosing date of Maintenance Study, for subjects who took any study treatment in Maintenance Study

Maintenance Study

Treatment-emergent laboratory abnormalities are defined as values that increase at least 1 toxicity grade from re-baseline at any time point after first dose of maintenance, up to 30 days after last dosing date of Maintenance Study.

Overall (Induction and Maintenance)

Treatment-emergent laboratory abnormalities are defined as values that increase at least 1 toxicity grade from baseline (Day 1) at any postbaseline time point, up to 30 days after permanent discontinuation of study drug of Induction or Maintenance study, whichever is later.

If the relevant baseline laboratory value is missing, any abnormality of at least Grade 1 observed within the time frame specified above will be considered treatment emergent.

7.2.2.2. Treatment-Emergent Marked Laboratory Abnormalities

Induction Studies (Cohort A Induction Study and Cohort B Induction Study)

Treatment-emergent marked laboratory abnormalities are defined as values that increase at least 3 toxicity grades from baseline at any postbaseline time point, and

- No later than 30 days after the last dosing date of Induction Study, for subjects who did not take any study treatment in the Maintenance Study, or
- On or before the first dosing date of Maintenance Study, for subjects who took any study treatment in the Maintenance Study

Maintenance Study

Treatment-emergent marked laboratory abnormalities are defined as values that increase at least 3 toxicity grades from re-baseline at any postbaseline time point after the first dose date of Maintenance Study, up to 30 days after permanent discontinuation of study drug.

Overall (Induction and Maintenance)

Treatment-emergent laboratory abnormalities are defined as values that increase at least 3 toxicity grades from baseline at any postbaseline time point, up to 30 days after permanent discontinuation of study drug of Induction or Maintenance study, whichever is later.

If the relevant baseline laboratory value is missing, any Grade 3 or 4 values observed within the timeframe specified above will be considered treatment-emergent marked abnormalities.

7.2.2.3. Summaries of Laboratory Abnormalities

Laboratory data that are categorical will be summarized using the number and percentage of subjects in the study with the given response at baseline and each scheduled postbaseline time point for Cohort A Induction Study, Cohort B Induction Study, and Cohorts A and B Induction Studies combined, and at re-baseline and each schedule time point afterwards for Maintenance Study.

The following summaries (number and percentage of subjects) for treatment-emergent laboratory abnormalities will be provided by lab test and treatment group for Cohort A Induction Study, Cohort B Induction Study, Cohorts A and B Induction Studies combined, Maintenance Study, and Overall; subjects will be categorized according to the most severe postbaseline abnormality grade for a given lab test:

- Graded laboratory abnormalities
- Grade 3 or higher laboratory abnormalities
- Marked laboratory abnormalities

For all summaries of laboratory abnormalities, the denominator is the number of subjects with nonmissing postbaseline values.

A by-subject listing of treatment-emergent Grade 3 or 4 laboratory abnormalities will be provided by subject ID number and time point in chronological order. This listing will include all test results that were collected throughout the study for the lab test of interest, with all applicable severity grades displayed.

7.2.3. Laboratory Evaluations of Interest

7.2.3.1. Liver-related Laboratory Evaluations

Liver-related abnormalities after initial study drug dosing will be examined and summarized using the number and percentage of subjects who were reported to have the following laboratory test values for postbaseline measurements for Cohort A Induction Study, Cohort B Induction Study, Cohorts A and B Induction Studies combined, and Maintenance Study:

- AST: (a) > 3 times of the upper limit of normal range (ULN); (b) > 5 x ULN; (c) > 10 x ULN; (d) > 20 x ULN
- ALT: (a) > 3 x ULN; (b) > 5 x ULN; (c) > 10 x ULN; (d) > 20 x ULN
- AST or ALT > 3 x ULN and total bilirubin > 2 x ULN

For individual laboratory tests, subjects will be counted once based on the most severe postbaseline values. For both the composite endpoint of AST or ALT and total bilirubin, subjects will be counted once when the criteria are met at the same postbaseline visit date. The denominator is the number of subjects in the Safety Analysis Set who have nonmissing postbaseline values of all relevant tests at the same postbaseline visit date. A listing of subjects who met at least 1 of the above criteria will be provided.

7.2.3.2. Complete Blood Count-Related Laboratory Evaluations

Complete blood count (CBC)-related abnormalities such as anemia, leucopenia, neutropenia, lymphopenia, and thrombocytopenia after initial study drug dosing will be examined and summarized using the number and percentage of subjects who were reported to have the following laboratory test values for postbaseline measurements for Cohort A Induction Study, Cohort B Induction Study, Cohorts A and B Induction Studies combined, and Maintenance Study:

- Hemoglobin: (a) postbaseline worsening CTCAE grade from baseline; (b) baseline value of less than Grade 3 and increase to Grade 3 or 4 at worst postbaseline; (c) baseline value of less than Grade 3 and increase to Grade 4 at worst postbaseline
- White blood cell (WBC) count: (a) postbaseline worsening CTCAE grade from baseline; (b) baseline value of less than Grade 3 and increase to Grade 3 or 4 at worst postbaseline; (c) baseline value of less than Grade 3 and increase to Grade 4 at worst postbaseline
- Absolute neutrophil count: (a) postbaseline worsening CTCAE grade from baseline; (b) baseline value of less than Grade 3 and increase to Grade 3 or 4 at worst postbaseline; (c) baseline value of less than Grade 3 and increase to Grade 4 at worst postbaseline
- Lymphocyte count: (a) postbaseline worsening CTCAE grade from baseline; (b) baseline value of less than Grade 3 and increase to Grade 3 or 4 at worst postbaseline; (c) baseline value of less than Grade 3 and increase to Grade 4 at worst postbaseline
- Platelet count: (a) postbaseline worsening CTCAE grade from baseline; (b) baseline value of less than Grade 3 and increase to Grade 3 or 4 at worst postbaseline; (c) baseline value of less than Grade 3 and increase to Grade 4 at worst postbaseline

For Maintenance Study, re-baseline will be used in the summaries described above.

7.2.4. Shifts Relative to the Baseline Value

Shift tables will be presented by showing change in CTCAE grade for hemoglobin, platelet count, white blood cell (WBC) count, absolute lymphocyte count, absolute neutrophils, fasting triglycerides, and fasting total cholesterol.

Shift tables will be presented by showing change in lab normal range (low, normal, and high) for hematocrit, absolute monocyte count, absolute eosinophil count, and absolute basophil count. In addition, shift tables for fasting LDL and HDL will be presented using the following National Cholesterol Education Program (NCEP) ATP III categories {[National Cholesterol Education Program \(NCEP\) 2001](#)}:

- For LDL (mg/dL): <100, 100-129, 130-159, 160-189, and ≥ 190
- For HDL (mg/dL): < 40, ≥ 40 to < 60, and ≥ 60

In all shift tables, the number and proportion of subjects for each category of each laboratory result will be summarized by its baseline/rebaseline category for Cohort A Induction Study, Cohort B Induction Study, Cohorts A and B Induction Studies combined, and Maintenance Study.

For the Induction Studies, shift tables will be presented for Week 10. For the Maintenance Study, shift tables will be presented for Weeks 26 and 58.

7.3. Body Weight and Vital Signs

Descriptive statistics will be provided by treatment group for body weight, BMI and vital signs (resting blood pressure [systolic blood pressure and diastolic blood pressure], respiratory rate, pulse and temperature) as follows for each Induction Study and combined:

- Baseline value
- Values at each postbaseline time point
- Change from baseline at each postbaseline time point

In addition, descriptive statistics will be provided by treatment group for Maintenance Study

- Re-baseline values
- Values at each postbaseline time point after re-baseline
- Change from re-baseline at each postbaseline time point after re-baseline

A baseline value will be defined as the last available value collected on or prior to the date of first dose of study drug. Change from baseline to a postbaseline visit will be defined as the postbaseline value minus the baseline value. A re-baseline value will be defined as the last measurement obtained on or prior to the date/time of first dose of study drug for the Maintenance Study, and change from re-baseline will be defined as the visit value minus the re-baseline value. Body weight and vital signs measured at unscheduled visits will be included for the baseline/re-baseline value selection.

In the case of multiple values in an analysis window, data will be selected for analysis as described in Section 3.8.3. No formal statistical testing is planned.

A by-subject listing of vital signs will be provided by subject ID number and time point in chronological order. Body weight, height, and BMI will be included in the vital signs listing, if space permits. If not, they will be provided separately.

7.4. Prior and Concomitant Medications

Medications reported at screening and during the study will be coded using the current version of the World Health Organization (WHO) Drug dictionary.

7.4.1. Prior Medications

Prior medications are defined as any medication taken before a subject took the first study drug at baseline/re-baseline.

General prior and UC-specific prior medications will be summarized separately by preferred name using the number and percentage of subjects for each treatment group and overall. A subject reporting the same medication more than once will be counted only once when calculating the number and percentage of subjects who received that medication. The summary will be ordered by preferred term in descending overall frequency. For drugs with the same frequency, sorting will be done alphabetically.

For the purposes of analysis, any medication with a start date prior to the first dosing date of study drug will be included in the prior medication summary regardless of when the stop date is. If a partial start date is entered the medication will be considered prior unless the month and year (if day is missing) or year (if day and month are missing) of the start date are after the first dosing date. Medications with a completely missing start date will be included in the prior medication summary, unless otherwise specified.

Summaries will be based on the Safety Analysis Set for Cohort A Induction Study, Cohort B Induction Study, Cohort A and B Induction Studies Combined, and Maintenance Study. No formal statistical testing is planned.

7.4.2. Concomitant Medications

General concomitant and UC-specific concomitant medications are defined as medications taken while a subject took study drug. Use of concomitant medications will be summarized by preferred name using the number and percentage of subjects for each treatment group. A subject reporting the same medication more than once will be counted only once when calculating the number and percentage of subjects who received that medication. The summary will be ordered by preferred term in descending overall frequency. For drugs with the same frequency, sorting will be done alphabetically.

First dosing date and last dosing date for Cohort A Induction Study, Cohort B Induction Study, and Maintenance Study have been defined in Section 3.8. For the purposes of analysis, any medication with a start date prior to or on the first dosing date of study drug and continued to take after the first dosing date, or started after the first dosing date but prior to or on the last dosing date of study drug will be considered concomitant medications. Medications started and stopped on the same day as the first dosing date or the last dosing date of study drug will also be considered concomitant. Medications with a stop date prior to the date of first dosing date of study drug or a start date after the last dosing date of study drug will be excluded from the concomitant medication summary. If a partial stop date is entered, any medication with the month and year (if day is missing) or year (if day and month are missing) prior to the date of first study drug administration will be excluded from the concomitant medication summary. If a partial start date is entered, any medication with the month and year (if day is missing) or year (if day and month are missing) after the study drug stop date will be excluded from the concomitant medication summary. Medications with completely missing start and stop dates will be included in the concomitant medication summary, unless otherwise specified. Summaries will be based on the Safety Analysis Set. No formal statistical testing is planned.

All prior and concomitant medications (other than per-protocol study drugs) will be provided in a by-subject listing sorted by subject ID number and administration date in chronological order.

7.5. Electrocardiogram Results

A shift table of the investigators' assessment of ECG results at each visit compared with baseline (or re-baseline) values will be presented by treatment group for each Induction Study, Cohort A and B Induction Studies Combined, and Maintenance Study using the following categories: normal; abnormal, not clinically significant; abnormal, clinically significant. The number and percentage of subjects in each cross-classification group of the shift table will be presented. Subjects with a missing value at baseline (or re-baseline) or postbaseline will not be included in the denominator for percentage calculation.

No formal statistical testing is planned.

A by-subject listing for ECG assessment results will be provided by subject ID number and time point in chronological order.

7.6. Other Safety Measures

A data listing will be provided for subjects who become pregnant during the study.

7.7. Changes From Protocol-Specified Safety Analyses

There are no deviations from the protocol-specified safety analyses.

8. PHARMACOKINETIC (PK) ANALYSES

8.1. PK Sample Collection

Sparse plasma PK samples will be collected prior to dose at Weeks 10 and 58, post dose at Week 4 (at least 30 minutes and up to 3 hours after dosing), and at any time at Week 26.

An optional PK Substudy will be performed in a subset of subjects. In the PK substudy, the daily dose of study drug should be administered in the clinic (at one visit between Week 2 and Week 10, inclusive), and additional PK samples should be collected predose and at 0.5, 1, 2, 3, 4, and 6 hours post dose to determine the steady-state PK of filgotinib and its metabolite GS-829845.

8.2. PK Analyses Related to Intensive PK Sampling

Steady-state PK will be determined in subjects in the PK Substudy analysis set. Concentrations of filgotinib and its metabolite GS-829845 in plasma will be determined using validated bioanalytical assays.

8.2.1. Estimation of PK Parameters

PK parameters will be estimated using Phoenix WinNonlin[®] software using standard noncompartmental methods. The linear/log trapezoidal rule will be used in conjunction with the appropriate noncompartmental model, with input values for dose level, dosing time, plasma concentration, and corresponding real-time values, based on drug dosing times whenever possible.

All predose sample times before time-zero will be converted to 0. Predose samples may also serve as the 24-hour post dose sample if appropriate.

For area under the curve (AUC), samples BLQ of the bioanalytical assays occurring prior to the achievement of the first quantifiable concentration will be assigned a concentration value of 0 to prevent overestimation of the initial AUC. Samples that are BLQ at all other time points will be treated as missing data in WinNonlin. The nominal time point for a key event or dosing interval (τ) may be used to permit direct calculation of AUC over specific time intervals. The appropriateness of this approach will be assessed by the PK scientist on a profile-by-profile basis.

Pharmacokinetic parameters such as AUC_{inf} , λ_z and $t_{1/2}$ are dependent on an accurate estimation of the terminal elimination phase of drug. The appropriateness of calculating these parameters will be evaluated upon inspection of PK data on a profile-by-profile basis by the PK scientist.

8.2.2. PK Substudy

PK parameters will be generated for all subjects in the PK substudy analysis set. The analyte presented in [Table 8-1](#) will be evaluated if data are available

Table 8-1. Study Treatments and Associated Analyte

Treatment Group	Treatment	Analyte
Treatment 1	Filgotinib (200 mg) tablet	Filgotinib, GS-829845
Treatment 2	Filgotinib (100 mg) tablet	Filgotinib, GS-829845

The analytes and parameters presented in [Table 8-2](#) will be used to evaluate the PK objectives of the study. The primary PK parameters are $[AUC_{\tau}]$ and C_{max} of filgotinib and GS-829845. The PK parameters to be estimated in this study are listed and defined in the [Appendix 7](#).

Table 8-2. PK Parameters for Each Analyte

Analyte	Parameters
Filgotinib	AUC_{last} , AUC_{τ} , C_{max} , T_{max} , C_{τ} , and CL_{ss}/F , if appropriate
GS-829845	AUC_{last} , AUC_{τ} , C_{max} , T_{max} , and C_{τ} , if appropriate

Individual subject concentration data and individual subject PK parameters for filgotinib and GS-829845 will be listed and summarized using descriptive statistics by treatment. Summary statistics (subject number [n], mean, SD, coefficient of variation [%CV], median, min, max, Q1, and Q3) will be presented for both individual subject concentration data by time point and individual subject PK parameters by treatment. Moreover, the geometric mean, 95% CI, and the mean and SD of the natural log-transformed values will be presented for individual subject PK parameter data.

Individual concentration data listings and summaries will include all subjects with concentration data. The sample size for each time point will be based on the number of subjects with nonmissing concentration data at that time point. The number of subjects with concentration BLQ will be presented for each time point. For summary statistics, BLQ values will be treated as 0 at predose and one-half of the lower limit of quantitation (LLOQ) for postdose time points.

Individual PK parameter data listings and summaries will include all subjects for whom PK parameter(s) can be derived. The sample size for each PK parameter will be based on the number of subjects with nonmissing data for that PK parameter.

The following tables will be provided for each analyte by treatment:

- Individual subject concentration data and summary statistics
- Individual subject plasma PK parameters and summary statistics

For the PK Substudy, the following figures may be provided for each analyte by treatment:

- Mean (\pm SD) concentration data versus time (on linear and semilogarithmic scales)
- Median (Q1, Q3) concentration data versus time (on linear and semilogarithmic scales)

Individual, mean, and median postdose concentration values that are \leq LLOQ will not be displayed in the figures and remaining points connected.

The following listings will be provided:

- PK sampling details by subject including actual dosing time and actual draw time, calculated time postdose of sample collection, differences in scheduled and actual draw times, sample age, and sample concentration

8.3. Statistical Analysis Methods

For both Pharmacokinetic Analysis Set (sparse PK) and Pharmacokinetic Substudy Analysis Set, individual subject concentration data for filgotinib and its metabolite GS-829845 will be listed and summarized using descriptive statistics (eg, sample size, arithmetic mean, geometric mean, coefficient of variation (%), standard deviation, median, minimum, and maximum) by treatment. For PK samples collected prior to dose, summary statistics will be generated at nominal visits and only the records with PK drawn \geq 22 hours and \leq 26 hours after the prior dose of study drug will be included. If the date/time of prior dose of study drug is missing, then the corresponding concentration records will be excluded from the summary. The number of subjects with concentration BLQ will be presented for each time point. For summary statistics, BLQ values will be treated as 0 at predose and one-half of the lower limit of quantitation (LLOQ) for postdose time points.

Plasma concentrations over time may be plotted in semi-logarithmic and linear formats as mean \pm standard deviation, and median (Q1, Q3) for PK substudy.

For PK substudy, individual PK parameters (C_{max} , T_{max} , C_{tau} , AUC_{last} , AUC_{tau} , and CL_{ss}/F , as applicable) for both filgotinib and GS-829845 will be listed and summarized using descriptive statistics. Molar ratio of GS-829845 to filgotinib exposures (AUC_{last} , AUC_{tau} , C_{max} , and C_{tau} , as applicable) will also be calculated and summarized. It can be expressed as GS-829845 exposure/filgotinib exposure \times (425.51/357.43). Moreover, the geometric mean, 95% CI, and the mean and SD of the natural log-transformed values will be presented for individual subject PK parameter data.

Additional PK analysis may be performed and exposure-response relationships may be explored.

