#### 6.4.4. Pharmacokinetics Assessments

The PK sample at Week 4 is collected post-dose (at least 30 minutes and up to 3 hours after study drug dosing). For this visit, it is preferred that study drug dosing is done in clinic. The PK sample at Weeks 26 can be collected at any time without regard to dosing. The PK sample at Weeks 10 and 58 are collected at pre-dose (within 2 hours prior to dosing).

Subjects who consent to the optional PK substudy will have additional plasma PK samples at any single visit from Week 2 to Week 10, collected pre-dose, and at 0.5, 1, 2, 3, 4 and 6 hours after supervised dosing in the clinic. If a sub-study PK sample is scheduled to be collected at the same time as a sparse PK sample, only one sample should be collected.

For all visits with PK sampling, the time of dose taken prior to and on the day of visit will be noted in the eCRF. Plasma concentrations of filgotinib and its metabolite (GS-829845) will be analyzed.

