### 8.3. Data Handling Conventions

Values for missing safety laboratory data will not be imputed. However, a missing baseline result will be replaced with a screening result, if available. If no pre-treatment laboratory value is available, the baseline value will be assumed to be normal (ie, no grade [Grade 0]) for the summary of graded laboratory abnormalities. If safety laboratory results for a subject are missing for any reason at a time point, the subject will be excluded from the calculation of summary statistics for that time point.

Values for missing vital signs data will not be imputed. However, a missing baseline result will be replaced with a screening result, if available.

PK concentration values and PK parameter values below the limit of quantitation (BLQ) will be presented as "BLQ" in the data listings. BLQ values that occur prior to the first dose will be treated as 0, BLQ values at all other time points will be treated as 1/2 of the lower limit of quantitation (LLOQ).

Laboratory data that are continuous in nature but are less than the LLOQ or above the upper limit of quantitation will be imputed to the value of the lower or upper limit minus or plus one significant digit, respectively (eg, if the result of a continuous laboratory test is < 20, a value of 19 will be assigned; if the result of a continuous laboratory test is < 20.0, a value of 19.9 will be assigned).

Procedures for handling missing data for MCS (and components) will be described in the SAP.

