1.2.3. Pharmacokinetics Substudy

An optional PK substudy will be performed in a subset of subjects (approximately 30 subjects each in Cohort A and Cohort B) who provide separate informed consent. In the PK substudy, the daily dose of study drug should be administered under supervision in the clinic (at 1 visit between Week 2 and Week 10, inclusive), and additional PK samples should be collected predose and at 0.5, 1, 2, 3, 4, and 6 hours post dose.

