Natural logarithm transformation will be used for plasma concentrations and analysis of PK parameters. Plasma concentration values that are below the limit of quantitation (BLQ) will be presented as “BLQ” in the concentration data listing. Values that are BLQ will be treated as 0 at predose time points, and one-half the value of the LOQ at postbaseline time points.

The following conventions will be used for the presentation of summary and order statistics:

- If at least 1 subject has a concentration value of BLQ for the time point, the minimum value will be displayed as “BLQ.”
- If more than 25% of the subjects have a concentration data value of BLQ for a given time point, the minimum and Q1 values will be displayed as “BLQ.”
- If more than 50% of the subjects have a concentration data value of BLQ for a given time point, the minimum, Q1, and median values will be displayed as “BLQ.”
- If more than 75% of the subjects have a concentration data value of BLQ for a given time point, the minimum, Q1, median, and Q3 values will be displayed as “BLQ.”
- If all subjects have concentration data values of BLQ for a given time point, all order statistics (minimum, Q1, median, Q3, and maximum) will be displayed as “BLQ.”

Pharmacokinetic parameters that are BLQ will be imputed as one-half LOQ before log transformation or statistical model fitting.

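### SAP 8.2.2 and 8.3 set below-quantitation predose concentrations to zero after dosing has begun, where the protocol assigns half the LLOQ; one such value breaks the geometric mean listed in SAP 8.3

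*SAP*

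**What the plan says.** **Protocol 8.3 (Data Handling Conventions)** divides samples at the first dose: "BLQ values that occur prior to the first dose will be treated as 0", and "BLQ values at all other time points will be treated as 1/2 of the lower limit of quantitation (LLOQ").

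**SAP 8.3**, for both the sparse and the substudy sets, divides them at the dose on the sampling day: "BLQ values will be treated as 0 at predose and one-half of the lower limit of quantitation (LLOQ) for postdose time points". SAP 8.2.2 repeats this for the substudy.

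**SAP 3.7** mixes the two: "Values that are BLQ will be treated as 0 at predose time points, and one-half the value of the LOQ at postbaseline time points". It also says: "Natural logarithm transformation will be used for plasma concentrations and analysis of PK parameters".

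**Sampling times.** SAP 8.1: "Sparse plasma PK samples will be collected prior to dose at Weeks 10 and 58, post dose at Week 4"; the Week 26 sample may be taken at any time. Protocol 6.4.4: "The PK sample at Weeks 10 and 58 are collected at pre-dose (within 2 hours prior to dosing"). The substudy profile, including its predose sample, is taken "at 1 visit between Week 2 and Week 10, inclusive" (SAP 1.2.3). The protocol's study procedures table shows no PK sample on Day 1.

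**Planned summaries.** SAP 8.3 names the geometric mean among example statistics for concentrations. It keeps a predose record only if the sample was drawn 22 to 26 hours after the previous dose.

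**The concern.** Zero is a natural value for a sample taken before any drug has been given. These predose samples are taken weeks into dosing. In a subject on filgotinib, a BLQ result there means a concentration somewhere between zero and the LLOQ, which is why the protocol uses half the LLOQ.

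The SAP departs from that rule without saying so. Its change sections cover efficacy (6.6) and safety (7.7), and its revision log (12) does not mention BLQ handling.

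The departure also clashes with the SAP's own statistics, because a zero has no logarithm. PK characteristics are an other secondary endpoint in both induction studies and in maintenance, so the trough tables will be read. Two programmers following the two documents would produce different tables.

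**Working it through.** The plan gives no figure to reproduce, so the check compares the rules and then sizes the effect.

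**Step 1. Which rule applies to each scheduled predose sample**

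| Predose sample | Before first dose? | Protocol 8.3 | SAP 8.2.2 / 8.3 | SAP 3.7 |
|---|---|---|---|---|
| Substudy visit, Weeks 2–10 | No | ½ LLOQ | 0 | 0 or ½ LOQ |
| Week 10 sparse | No | ½ LLOQ | 0 | 0 or ½ LOQ |
| Week 58 sparse | No | ½ LLOQ | 0 | 0 or ½ LOQ |

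The protocol's zero rule applies to no scheduled sample. The zero rule in SAP 8.2.2 and 8.3 applies to all of them.

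**Step 2. Effect on the geometric mean, GM = exp(mean of ln x)**

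Take 12 subjects, roughly one filgotinib dose group in one cohort's substudy (30 × 2/5 = 12 at 2:2:1). Assume LLOQ = 1 and every quantifiable trough equal to 5.

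| BLQ values | GM, BLQ = 0 | GM, zeros dropped | GM, ½ LLOQ | Arithmetic mean, 0 | Arithmetic mean, ½ LLOQ |
|---|---|---|---|---|---|
| 1 of 12 | 0 or undefined | 5.00 | (5¹¹ × 0.5)^(1/12) = 4.13 | 55/12 = 4.58 | 55.5/12 = 4.63 |
| 3 of 12 | 0 or undefined | 5.00 | (5⁹ × 0.5³)^(1/12) = 2.81 | 45/12 = 3.75 | 46.5/12 = 3.88 |

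**Step 3. Bias under an assumed distribution**

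Assume log-normal troughs with a 100% CV, so σ = √ln 2 = 0.8326, and set the true GM to 1. Let p be the BLQ share, z the standard normal p-quantile and φ the normal density at z.

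- Zeros dropped: GM = exp[σφ/(1 − p)]
- ½ LLOQ: GM = exp[p(σz − ln 2) + σφ]
- Arithmetic mean with zeros: A = exp(σ²/2) × [1 − Φ(z − σ)]. With ½ LLOQ it is A + p × exp(σz)/2.

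| p | z | φ | GM, zeros dropped | GM, ½ LLOQ | Arithmetic mean, 0 relative to ½ LLOQ |
|---|---|---|---|---|---|
| 5% | −1.645 | 0.103 | 1.09 (+9%) | 0.98 (−2%) | −0.5% |
| 20% | −0.842 | 0.280 | 1.34 (+34%) | 0.96 (−4%) | −4% |
| 40% | −0.253 | 0.386 | 1.71 (+71%) | 0.96 (−4%) | −12% |

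**Step 4. How easily a cell is affected**

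P(at least one BLQ) = 1 − (1 − q)ⁿ, where q is the assumed chance that a single sample is BLQ. For n = 12 and q = 1%, 5%, 10%, 20% this is 0.11, 0.46, 0.72, 0.93. For n = 260, a full induction dose group with every sample evaluable, it is already 0.93 at q = 1%.

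**Step 5. What is outside the problem**

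SAP 3.7 sets BLQ PK parameters to half the LOQ before log transformation. SAP 8.2.1 has a separate BLQ rule for AUC. One inconsistency follows: SAP 8.2.1 lets a predose sample stand in for the 24-hour value, so the same BLQ result could appear as 0 in the concentration table and as half the LOQ if reported as Ctau.

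**The case against.** The strongest reply is that little depends on this, and most of that reply stands.

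- **It is conditional.** The geometric mean fails only in a cell with at least one BLQ predose value. The documents give no LLOQ, trough levels or human half-life for filgotinib or GS-829845, so the frequency is unknown. Every BLQ share and the CV above are assumptions.
- **Few geometric means are exposed.** SAP 8.2.2 plans geometric means only for PK parameters. For concentrations they appear only in SAP 8.3, in a list of examples, as in protocol 8.7. However, SAP 8.3 covers the substudy concentrations too.
- **The result would be visible.** The number of BLQ subjects is reported at each time point, and the order statistics display as BLQ as the share rises. A reader would be warned, but the mean would still be wrong.
- **SAP 3.7 can be read to agree with the protocol**, if predose there means before the first dose. It therefore needs clarifying rather than reversing.
- **Dropping zeros is not planned.** The SAP does not say how a zero enters a geometric mean; 9% to 71% describes one possible software behaviour.

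A reader might also infer that every predose sample is an on-treatment filgotinib trough. That goes too far. Responders re-randomized to placebo have a scheduled Week 58 sample, and the 22-to-26-hour filter counts from the previous dose of study drug, which includes placebo.

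**Conclusion.** The inconsistency is real and rests on no assumption: SAP 8.2.2 and 8.3 assign zero to samples for which protocol 8.3 assigns half the LLOQ, and all scheduled predose samples are of that kind. SAP 3.7 does not settle which rule holds.

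The consequence is conditional. With one or more BLQ predose values in a cell, the SAP 8.3 geometric mean concentration is zero or undefined. If zeros are dropped, it is about 9% to 71% too high for BLQ shares of 5% to 40%, against an error of about −2% to −4% with half the LLOQ. Arithmetic means fall by about 0.5% to 12% relative to half the LLOQ. These figures assume log-normal troughs with a 100% CV.

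A reader might conclude that the planned PK geometric means in general, or the PK secondary endpoint as a whole, are compromised. The documents do not support that. Parameter geometric means are protected by SAP 3.7, AUC has its own rule in SAP 8.2.1, and no efficacy inference is touched. This is a minor correction to descriptive concentration summaries.

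**What to change.** In SAP 8.2.2 and 8.3, replace the predose/postdose split with the protocol rule: a BLQ concentration is 0 only before the first dose of study drug, and half the LLOQ at every later time, including predose samples. Reword SAP 3.7 to say the same, dropping the overlapping predose and postbaseline terms.

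If the sponsor prefers zero for these samples, the SAP should declare this as a change from the protocol and state how the geometric mean handles zeros.

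The cost is one sentence in each of three SAP sections and the matching line of code. Sampling, analysis sets and efficacy analyses do not change.
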